## 14.10.5. Safety Tables

| Safety: Tables                |             |                      |   |  |             |
|-------------------------------|-------------|----------------------|---|--|-------------|
| No.                           | Population  | IDSL / Example Shell | Title   | Programming Notes  | Deliverable |
| Adverse Events (AEs)   |             |                      |   |  |             |
| 3.1.                          | All Treated | AE5B                 | Summary of All Adverse Events by System Organ Class and Preferred Term and Maximum Grade  | ICH E3   | SAC         |
| 3.2.                          | All Treated | AE5B                 | Summary of All GSK3368715-Related Adverse Events by System Organ Class and Preferred Term and Maximum Grade                                   | ICH E3   | SAC         |
| 3.3.                          | All Treated | AE15                 | Summary of Common ( $\geq 5\%$ ) Non-serious Adverse Events by System Organ Class and Preferred Term (Number of Participants and Occurrences) | FDAAA, EudraCT   | SAC         |
| 3.4.                          | All Treated | AE3                  | Summary of Adverse Events Leading to Dose Reductions  |  | SAC         |
| 3.5.                          | All Treated | AE3                  | Summary of Adverse Events Leading to Dose Interruptions   |  | SAC         |
| Serious Adverse Events |             |                      |   |  |             |
| 3.6.                          | All Treated | AE16                 | Summary of Serious Adverse Events by System Organ Class and Preferred Term (Number of Participants and Occurrences)                           | FDAAA, EudraCT   | SAC         |
| 3.7.                          | All Treated | AE3                  | Summary of Adverse Events Leading to Permanent Discontinuation of Study Treatment by Overall Frequency  | IDSL   | SAC         |
| 3.8.                          | All Treated | AE3                  | Summary of Drug-Related Serious Adverse Events  |  | SAC         |
| Deaths                 |             |                      |   |  |             |
| 3.9.                          | All Treated | DTH1a                | Summary of Deaths   | IDSL
Report time to death from last dose (in days) as in the mock | SAC         |

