Number of Participants: It is estimated that up to approximately 60 participants will be enrolled in Part 1. In Part 2, approximately 141 participants will be recruited into Expansion Cohort 2A (~36 participants) and Expansion Cohort 2B (~ 105 participants). Additional tumor-specific cohort(s) and combinations may be added by protocol amendment, based upon emerging pre-clinical data, or clinical data.

Intervention Groups and Duration: In Part 1 of the study, the participants will initially receive GSK3368715 orally. This will include at least one PK/PD cohort and a food effect cohort. The Dose Limiting Toxicity (DLT) period is 21 days, and under protocol amendment 3, there is an addition of a VTE-specific DLT period of 8 (\pm 1) weeks or until study discontinuation whichever occurs sooner. An end of treatment CT image is required if the participant withdraws before the end of the DLT observation period. Alternative dosing schedules and intervention cycles may be investigated. In Part 2, the participants are expected to receive the RP2D established in Part 1. In case of unexpected toxicities, alternative GSK3368715 doses may be explored in Part 2.

The study includes a screening period, an intervention period and follow up. Participants will be screened for eligibility beginning approximately 4 weeks before the start of intervention. Participants with confirmed partial response (PR) or complete response (CR) will be followed for response duration and may be eligible for additional intervention with GSK3368715 at the time of relapse/progression if determined to be deriving clinical benefit in the opinion of the investigator and with approval from the study Medical Monitor.

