Telemetry	X				X								Telemetry only required for doses > 200 mg and must start at least 60 min pre-dose and be continuous for 24h post-dose. See Section 8.2.5.
Holter monitoring	X				X		X		X				Holter monitoring must start at least 60 min pre-dose and be continuous for 24h post-dose.
12-lead ECG (Triplicate)	X	X	X		X		X		X	Q1W	X		On serial PK days (Day 1, 8 and 15), triplicate ECGs will be obtained at or about the time of each PK sample collection, as described in the SRM. On other days, triplicate ECGs will be obtained pre-dose.
Laboratory Assessments (Safety) – perform assessments pre-dose on each dosing day													
Clinical Chemistry, Urinalysis and Coagulations	X				X		X		X	Q1W	X		Refer to Appendix 2 for complete list of required laboratory assessments.
Hematology	X			X	X	X	X		X	Q1W	X		Hematology twice per week for the first two weeks (see Section 2.3.1). Refer to Appendix 2 for complete list of required laboratory assessments.
Pregnancy test					X				X	Q4W	X		Perform only in women of child bearing potential (WOCBP). Pregnancy tests during intervention phase and at discontinuation may be either serum

Procedure	DLT period (Days 1-21) ³								D22 ³	Continuation ³	TDV ¹	Follow-up	Notes		
	D1 ²	D2	D3	D4	D8	D11	D15	D16							
													or urine. Final pregnancy test must be performed within 150 days after last study intervention.		
Study intervention															
Administer study drug	X			←=====Daily Dosing=====→											A dose will be administered on Day 1, no dose will be given on Day 2 or Day 3 of the first cycle, after which, daily dosing will occur through the remainder of cycle 1 and all subsequent cycles. GSK3368715 should be administered in a fasted state at approximately the same time of day (\pm 4 h), with no food for 1 hour before and 2 hours after each dose. See Section 5.3.1 for dosing instructions on serial PK days.
Efficacy Assessment															
Tumor Imaging. Must include CT Chest. Must include CT abdomen if history of documented intraabdominal disease.										Week 9 Day1 then every 8 weeks until Week 33 Day 1 and then Q16W	X		Disease assessments will be performed until disease progression. Participants who discontinue for reasons other than PD will also be followed until the start of subsequent anti-cancer intervention. CR or PR should be confirmed as per response criteria in Appendix 10 .		
Patient Reported Outcomes															

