Due to the observed incidence of embolic and thrombotic events, the study was put on enrolment pause and protocol amendment 3 now includes additional guidelines for management and stopping criteria for VTE..

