Thromboembolic Risk	A higher than expected incidence of venous thromboembolism was observed in the first 19 participants treated on clinical study 207675.	
 • Change in inclusion/exclusion criteria, to exclude participants at high risk of VTE. • Extended monitoring time for VTE events to clear dose prior to dose escalation. • Include cohort stopping rules for VTE • Resume enrollment under protocol amendment 03 at reduced dose of 100 mg po daily • Limit dose escalation to 50 mg increments.
Study procedures		
Biopsy	A tissue biopsy is required in PK/PD cohorts to evaluate tumor expression of the biomarkers pathway. Risks associated with a tumor biopsy depend upon the location and type of biopsy performed. Pain, infection, bleeding may occur after the procedure. Additional risks depending on the location of the biopsy may include pneumothorax, pneumonia, injury to surrounding nerves or organs, hospitalization, and, rarely, death.	
 • Participants will be informed of the specific risks associated with the biopsy to be performed through the ICF. Participants at increased risk or not well suited to undergo a biopsy should not be enrolled in a cohort that requires a fresh biopsy. Participants will be treated according to local practice.

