4.1.3. Dose-Limiting Toxicity

All toxicities will be graded using National Cancer Institute – Common Toxicity Criteria for Adverse Events (NCI-CTCAE), version 5.

An AE is considered to be a dose-limiting toxicity (DLT) if the event is considered by the investigator to be clinically relevant and attributed (definitely, probably or possibly) to the study intervention during the first 21 days of intervention and meets at least one of the criteria listed in [Table 6](#).

In addition, there are clear VTE DLT criteria:

- Upon re-initiation of enrolment under Protocol Amendment 3, any cohort in Part 1 with two (2) grade 2 venous thromboembolism (VTE) that requires systemic anticoagulation or \geq grade 3 VTE in up to 6 participants will be considered not cleared and enrolment at this dose level and higher dose levels will be permanently stopped.
- Upon re-initiation of enrolment under Protocol Amendment 3, any cohort in Part 1 with ≥ 3 grade 2 venous thromboembolism (VTE) that requires systemic anticoagulation or Grade ≥ 3 VTEs out of up to 10 participants will be considered not cleared and enrolment at this dose level and higher dose levels will be permanently stopped.
- Upon re-initiation of enrolment under Protocol Amendment 3 at 100mg, dose escalation steps will be considered in maximal steps of 50 mg depending on the pharmacodynamic effects and the safety profile observed in previous cohorts, taking into consideration the updated DLT criteria (see [Table 6](#)).
- Grade 2 venous thromboembolism (VTE) that requires systemic anticoagulation or \geq grade 3 VTE, regardless of investigator assessed causality, will be considered a DLT during the first 8 (± 1) weeks or until study discontinuation (e.g., disease progression), whichever occurs sooner.
- An end of treatment CT image is required if the participant withdraws before the end of the VTE DLT observation period ([Table 6](#)).

If an AE is considered related to the underlying disease it is not defined as a DLT.

Table 6 Dose-Limiting Toxicity Criteria

DLT criteria for Non-hematologic Toxicity	
AST or ALT	
 • Grade 3 • Grade 4 • ALT \geq 5xULN • ALT \geq 3xULN persists for \geq 4 weeks • ALT \geq 3xULN and bilirubin \geq 2xULN (>35% direct bilirubin) • ALT \geq 3xULN and INR >1.5, if INR measured • ALT \geq 3xULN associated with symptoms (new or worsening) believed to be related to liver injury or hypersensitivity

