8.1. Efficacy

- Disease assessment modalities may include imaging (e.g., computed tomography [CT] scan, magnetic resonance imaging [MRI], bone scan, plain radiography) and physical examination (as indicated for palpable/superficial lesions).
- The baseline disease assessment will be completed within 4 weeks prior to the first dose of GSK3368715, then after 8 weeks of dosing (week 9 day 1) and every 8 weeks thereafter until the end of week 32 then every 16 weeks, until disease progression. See the SoA (Section 1.3 Table 2) for the schedule of assessments of anticancer activity.
- Assessments must be performed on a calendar schedule and should not be affected by dose interruptions/delays.
- For post-baseline assessments, a window of ± 7 days is permitted to allow for flexible scheduling. If the last radiographic assessment was 8 weeks or more prior to the participant's withdrawal from study intervention and PD has not been documented, a disease assessment should be obtained at the time of withdrawal from the study intervention.
- Participants whose disease responds (either complete response [CR] or partial response [PR]) should have a confirmatory disease assessment performed at least 4 weeks after the date of assessment during which the response was

demonstrated. More frequent disease assessments may be performed at the discretion of the investigator.

- To ensure comparability between the baseline and subsequent assessments, the same method of assessment and the same technique will be used when assessing response.

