8.4.2. Cardiovascular and Death Events

For any cardiovascular events and all deaths, whether or not they are considered SAEs, specific Cardiovascular (CV) and Death sections of the CRF will be required to be completed. These sections include questions regarding cardiovascular (including sudden cardiac death) and non-cardiovascular death.

The CV CRFs are presented as queries in response to reporting of certain CV MedDRA terms. The CV information should be recorded in the specific cardiovascular section of the CRF within one week of receipt of a CV Event data query prompting its completion.

The Death CRF is provided immediately after the occurrence or outcome of death is reported. Initial and follow-up reports regarding death must be completed within one week of when the death is reported.

A CV event is defined as:

- Myocardial infarction/unstable angina
- Congestive heart failure
- Arrhythmias
- Valvulopathy
- Pulmonary hypertension

- Cerebrovascular events/stroke and transient ischemic attack
- Peripheral arterial thromboembolism
- Deep venous thrombosis/pulmonary embolism
- Revascularization

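### No planned SAP table counts participants with any venous thromboembolism (VTE) by dose, and the period covered by the DLT table is undefined

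*SAP*

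**What the plan says.** **Why VTE is central.** Protocol 2.2.1.4.2: "Due to the observed incidence of embolic and thrombotic events, the study was put on enrolment pause". The risk table in protocol 2.3.1 adds: "A higher than expected incidence of venous thromboembolism was observed in the first 19 participants treated on clinical study 207675".

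**How cohorts are assessed.** Under protocol 4.1.3, a cohort with two VTEs that are Grade 2 needing systemic anticoagulation, or at least "grade 3 VTE in up to 6 participants will be considered not cleared". A second threshold is three or more among up to 10 participants. SAP 2.3 repeats both. Neither separates types of VTE.

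**The DLT windows.** The general DLT window is 21 days. The protocol synopsis says that "under protocol amendment 3, there is an addition of a VTE-specific DLT period of 8" (±1) weeks, or until study discontinuation if sooner. SAP 2.3 restates this window and applies it regardless of causality. SAP 3.1 describes the DLT evaluation period as the first 21 days.

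**Imaging.** Protocol Table 2 requires tumour imaging that includes a chest CT at "Week 9 Day1 then every 8 weeks until Week 33 Day 1 and then Q16W". Protocol 8.1 adds: "For post-baseline assessments, a window of ± 7 days is permitted to allow for flexible scheduling".

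**What will be reported.** SAP Appendix 10 lists Tables 3.1 to 3.24 and Listings 1 to 39. Table 3.1 is the "Summary of All Adverse Events by System Organ Class and Preferred Term and Maximum Grade". No title names VTE or any grouped event. DLTs, a Part 1 primary endpoint, go into Table 3.22 and Listing 22 over a 'Determinative Period'. The term appears only in those two titles. Protocol 8.4.2 has one cardiovascular CRF category for "Deep venous thrombosis/pulmonary embolism", but no SAP display uses it.

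**The concern.** There are two gaps, of unequal weight.

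The main one is the missing count. With enrolment closed, the final report is where VTE frequency by dose should be stated. The planned tables offer three counting levels: preferred term, organ class and any event. None equals any VTE. The rate would therefore be assembled by hand from Listings 14 and 15 by someone who already knows the results and must decide which terms belong.

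The smaller one is the DLT period. Table 3.22 and Listing 22 carry a primary endpoint, and the SAP does not say whether their period is 21 days or the longer VTE window. On a 21-day reading, a VTE that the protocol's Table 6 calls a DLT could be absent from the DLT table.

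The two interact. If the VTE criterion applies only from Amendment 3, the earlier VTEs that caused the pause enter Table 3.22 only under the general rule (attributed to drug, within 21 days). A grouped table would then be the only display that counts earlier and later VTEs together.

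**Working it through.** **1. The cohort rule runs on one pooled count.** Protocol 9.2.1.1 stops a cohort at 2 or more VTEs among 6 or fewer participants, or 3 or more among 7 to 10. With X_n the number of VTEs among n participants and true rate p:

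P(stop) = P(X_6 ≥ 2) + P(X_6 = 0)·P(X_4 ≥ 3) + P(X_6 = 1)·P(X_4 ≥ 2)

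At p = 0.30: 0.5798 + 0.1176 × 0.0837 + 0.3025 × 0.3483 = 0.5798 + 0.0098 + 0.1054 = 0.695.

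| True VTE rate | Protocol Table 8 | Exact |
|---|---|---|
| 5% | 3.8% | 3.6% |
| 10% | 13.6% | 13.5% |
| 15% | 26.9% | 27.2% |
| 20% | 42.1% | 42.3% |
| 25% | 56.8% | 56.8% |
| 30% | 69.5% | 69.5% |

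The largest gap is 0.3 points, as expected from simulation. Table 8 is sound, and the quantity behind it is a single VTE count per cohort.

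**2. Preferred-term rows do not return that count.** SAP 8.2 counts a participant once within each term. Take a hypothetical cohort of 10 with a deep venous thrombosis row of 2 and a pulmonary embolism row of 2. If the same two people had both, 2 participants had a VTE. If one person had both, it is 3. If there is no overlap, it is 4. The rows sum to 4 in every case, and the possible answers straddle the threshold of 3.

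Without overlap the rows do sum correctly, but no line shows the total. Three participants in 10 with three different terms (30.0%, exact 95% CI 6.7 to 65.2) would appear as three rows of 1/10 (10.0%, 0.3 to 44.5). These counts are illustrations only. With a single term in use, the row is the answer and nothing is understated.

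**3. Timing of the scan against a 21-day table.**

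- Week 9 Day 1 = (9 − 1) × 7 + 1 = study day 57; ±7 days gives days 50 to 64.
- Days after day 21: 57 − 21 = 36, with a range of 50 − 21 = 29 to 64 − 21 = 43.
- Time from Day 1: 56 days (49 to 63), or 8 (7 to 9) weeks, in line with the 8 (±1) week VTE window.

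A VTE first found on that scan always falls after day 21. It usually falls within the VTE window, but not always. Counting Day 1 as the first day, nine weeks ends on day 63, so a scan on day 64 is outside. Study discontinuation can also close the window sooner.

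**4. Possible size of a 21-day omission.** The documents do not give the share of VTEs arising after day 21. As an assumption, let it be 25% to 75%. At a true 8-week rate of 30%, 10 participants have 10 × 0.30 = 3.0 expected qualifying VTEs. A 21-day table would omit 3.0 × 0.25 = 0.75 to 3.0 × 0.75 = 2.25 of them. At a 10% rate the figures are 0.25 to 0.75 of 1.0.

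**The case against.** The case on the other side is substantial.

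- **The SAP follows the protocol.** Protocol 9.6.2.2 promises summaries by preferred term and DLTs by dose cohort, and the SAP provides both. This stands: a reader might infer that a promised analysis has been dropped, and the documents do not support that. Nor does any dose decision now depend on the table, since enrolment has ended.
- **No data are lost.** Listing 14 gives all adverse events, Listing 15 gives subject numbers for each event, and VTEs may also appear in Tables 3.6 to 3.8. This stands too. The gap is in tabulation. What the listings cannot supply is a term list fixed in advance.
- **Term rows fail to sum only when one participant has more than one VTE term.** Correct. It would be too strong to say that having several terms alone defeats the sum.
- **The 21-day reading may not be the natural one.** SAP 2.3 already tells an analyst that a qualifying VTE within 8 (±1) weeks is a DLT, and SAP 3.1.1 points to the protocol's DLT criteria. SAP 3.1 concerns the timing of escalation meetings. A reader might infer that Table 3.22 will omit late VTE DLTs, but the documents do not say so. The omission is conditional on one reading of an undefined term.
- **The sponsor's standard shells are not in the documents.** They might define the period, or tabulate DLTs by criterion, in which case Table 3.22 could group the qualifying VTEs. Even then it would not count VTEs outside the DLT criteria.

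**Conclusion.** The point holds as a cheap and worthwhile improvement to the SAP. No planned table gives the number of participants with any VTE by dose, although VTE paused the study and the cohort rule uses a pooled count. The three counting levels in SAP 8.2 do not supply it, and Table 3.22 would show at most the DLT-qualifying subset.

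The undefined period is the lesser part and is closer to a clarification. It becomes a material omission from a primary-endpoint table only if 21 days is applied, and that would contradict SAP 2.3.

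The effect on actual results is unknown, because the available text gives neither the number of VTEs nor the terms used. The counts in the working are illustrations, and the 25% to 75% late share is an assumption. It would go too far to conclude that VTEs are hidden, that the true rate will be understated, or that every VTE seen on the Week 9 scan is a DLT.

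One question stays open. The synopsis and most of the wording in protocol 4.1.3 tie the VTE rules to Amendment 3, but the causality-free DLT item in 4.1.3, the VTE row of Table 6 and SAP 2.3 carry no such limit.

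**What to change.** 1. In SAP 8.2 and Appendix 10, add one table and a supporting listing of participants with any VTE, each counted once. Use a term list fixed before database freeze. Show the counts by initial dose (the SAP 5.2 convention) and overall, and by maximum grade. Include a row for VTEs meeting the Table 6 criterion and a split by enrolment before or after Amendment 3.

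2. As a clarification, state the Determinative Period for Table 3.22 and Listing 22: 21 days for general DLTs; for VTE DLTs, the first 8 (±1) weeks or until study discontinuation, whichever is sooner, regardless of causality. Confirm in the same place whether the VTE criterion applies only to participants enrolled under Amendment 3.

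The cost is one extra table, one extra listing, a short definition and the work of agreeing the term list. The adverse event and cardiovascular CRF data are already collected, and the protocol does not need to change.

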**CONFIDENTIAL**

207675

| Safety: Tables               |                   |                                 |   |                          |                    |
|-------------------------------------|-------------------|---------------------------------|---|--------------------------|--------------------|
| No.                          | Population | IDSL /
Example Shell | Title  | Programming Notes | Deliverable |
| Laboratory: Chemistry        |                   |                                 |   |                          |                    |
| 3.10.                               | All Treated       | LB1                             | Summary of Chemistry Changes from Baseline                                    | ICH E3                   | SAC                |
| 3.11.                               | All Treated       | LB18                            | Summary of Chemistry Grade Changes from Baseline                              | ICH E3                   | SAC                |
| 3.12.                               | All Treated       | LB3                             | Summary of Chemistry Changes from Baseline with Respect to the Normal Range   | ICH E3                   | SAC                |
| Laboratory: Haematology      |                   |                                 |   |                          |                    |
| 3.13.                               | All Treated       | LB1                             | Summary of Haematology Changes from Baseline                                  | ICH E3                   | SAC                |
| 3.14.                               | All Treated       | LB18                            | Summary of Haematology Grade Changes from Baseline                            | ICH E3                   | SAC                |
| 3.15.                               | All Treated       | LB3                             | Summary of Haematology Changes from Baseline with Respect to the Normal Range | ICH E3                   | SAC                |
| ECG                          |                   |                                 |   |                          |                    |
| 3.16.                               | All Treated       | EG1                             | Summary of ECG Findings   | IDSL                     | SAC                |
| 3.17.                               | All Treated       | EG2                             | Summary of Change from Baseline in ECG Values by Visit                        | IDSL                     | SAC                |
| Vital Signs                  |                   |                                 |   |                          |                    |
| 3.18.                               | All Treated       | VS1                             | Summary of Change from Baseline in Vital Signs                                | ICH E3                   | SAC                |
| Dose Modifications           |                   |                                 |   |                          |                    |
| 3.19.                               | All Treated       | ODMOD1                          | Summary of Dose Reductions of GSK3368715                                      | ICH E3                   | SAC                |
| 3.20.                               | All Treated       | ODMOD2                          | Summary of Dose Interruptions of GSK3368715                                   | ICH E3                   | SAC                |
| 3.21.                               | All Treated       | ODMOD8                          | Summary of Dose Escalations of GSK3368715                                     | If applicable.           | SAC                |
| Dose Limiting Toxicity (DLT) |                   |                                 |   |                          |                    |
| 3.22.                               | All Treated       | DL1                             | Summary of Dose-Limiting Toxicities during the Determinative Period           | ICH E3                   | SAC                |

| Safety: Tables            |             |                      |  |                   |             |
|---------------------------|-------------|----------------------|--|-------------------|-------------|
| No.                       | Population  | IDSL / Example Shell | Title  | Programming Notes | Deliverable |
| Performance Status |             |                      |  |                   |             |
| 3.23.                     | All Treated | PS1A                 | Summary of ECOG Performance Status                         | ICH E3            | SAC         |
| 3.24.                     | All Treated | PS3A                 | Summary of Change in ECOG Performance Status from Baseline |                   | SAC         |

